5. STUDY PROCEDURES

The study will be conducted at SCH in Suzhou, Jiangsu province. SCH is located in the central area of Gusu district and is the only tier III children's hospital serving most of the young children in Suzhou.

Children who are residents from Suzhou municipal districts (Gusu, New and high-tech, Wuzhong, Xiangcheng, Industrial Park) admitted to the SCH with diagnosis of clinical pneumonia per SCH local standard will be evaluated by investigator.

Inclusion and exclusion criteria will be evaluated and those that fulfill all inclusion criteria and none of the exclusion criteria will be offered to participate in the study. Once Informed Consent has been obtained from parents or legal guardians of participants (vaccinated patient and control), study procedures may start.

If a patient is eligible for this study, all study-related procedures will be conducted by study personnel within one day. For every study subject enrolled in the 13vPnC cohort, two study subjects that did not receive 13vPnC will be enrolled on the same day (or \pm 7 days) into the unvaccinated cohort. These control subjects will be matched by age (5 to \leq 12 months, $>$ 12 to \leq 24 months, $>$ 24 months to \leq 60 months). In other words, for every subject enrolled in the 13vPnC cohort, two subjects within the same age group who did not receive 13vPnC will be enrolled if the non-13vPnC subjects hospital admission dates are within 7 days (\pm) of the vaccinated subjects.

Treatment and non-study procedures will be provided by the patient's physician as per local standard of care.

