6.2.2.1.2. MOPA Assessments

Serum levels of MOPA for each of the 13 pneumococcal serotypes (1, 3, 4, 5, 6A, 6B, 7F, 9V, 14, 18C, 19A, 19F, and 23F) will be determined in all 13vPnC cohort subjects with adequate blood volume. In the non 13vPnC cohort, a sample of subjects with adequate blood volume will be selected, to be equal to the number of the 13vPnC cohort included for MOPA testing. Further details regarding the selection of this sub-cohort to be identified for MOPA testing will be outlined in the Statistical Analysis Plan (SAP).

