3. ENDPOINTS AND BASELINE VARIABLES: DEFINITIONS AND CONVENTIONS

3.1. Primary Endpoint(s)

The serotype-specific IgG geometric mean concentration (GMC) and MOPA geometric mean titers (GMT) for each of the pneumococcal serotypes measured at the time of diagnosis of clinical pneumonia.

Serum levels of MOPA for each of the 13 pneumococcal serotypes (1, 3, 4, 5, 6A, 6B, 7F, 9V, 14, 18C, 19A, 19F, and 23F) will be determined in all 13vPnC cohort subjects with adequate blood volume. In the non 13vPnC cohort, a sample of subjects with adequate blood volume will be selected, to be equal to the number of the 13vPnC cohort included for MOPA testing. This sample of subjects from Non-13vPnC cohort will be performed by randomly ordering all subjects with adequate serum volume and selecting the first number of subjects which is equal to the number of the 13vPnC cohort included for MOPA testing.

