5.2.2. Analyses for Continuous Endpoints

For each of the 13 serotypes contained in 13vPnC Cohort and also Non-13vPnC Cohort, GMCs of IgG and GMT of MOPA will be calculated along with 2-sided 95% CIs, which will be constructed by back transformation of the CIs for the mean of the logarithmically transformed IgG/MOPA computed using Student's t distribution. In addition, the 2-sided 95% CI on the geometric mean ratios (GMRs) (the GMC of 13vPnC Cohort to the GMC of Non-13vPnC Cohort and the GMT of 13vPnC Cohort to the GMT of Non-13vPnC Cohort) for all 13 serotypes will be also provided and those 95% CIs will be constructed by back transformation of the CIs for the mean difference of the measures on the logarithmically transformed scale(IgG/MOPA) using Student's t distribution.

A multiple regression model will be used with the log concentration or log titers as a dependent variable. Independent variables will include cohort (13vPnC or unvaccinated), 13vPnC VT carriage status, and the interaction of the cohort and carriage status, as well as the confounding variables (age at enrollment, sex, season of enrollment). Adjusted GMCs (or GMTs) and adjusted geometric mean ratios (GMRs) along with 95% CI will be estimated based on this model. The (GMRs) will compare antibody levels between:

1. Within 13vPnC Cohort: VT-carrier + vs VT-carrier -
2. Within Non-13vPnC Cohort: VT-carrier + vs VT-carrier -
3. 13vPnC Cohort vs Non-13vPnC Cohort
4. Within VT-carrier +: 13vPnC Cohort vs Non-13vPnC Cohort
5. Within VT-carrier -: 13vPnC Cohort vs Non-13vPnC Cohort

Additionally, serotype-specific GMC/GMT (unadjusted) and associated 95% CI will be provided for each 13vPnC VT carriage status (Yes/No), for both 13vPnC cohort and unvaccinated cohort. GMRs (unadjusted) (GMC/GMT of VT- carrier + vs GMC/GMT of VT-carrier -) within 13vPnC Cohort and within unvaccinated Cohort, and GMRs (unadjusted) (GMC/GMT of 13vPnC Cohort vs GMC/GMT of Non-13vPnC Cohort) within

VT-carrier + group and within VT-carrier group and associated 95% CIs will be calculated using Student's t distribution for the mean difference of the measures on the logarithmically transformed scale (IgG/MOPA).

If model adjusted GMCs, GMTs, GMRs are not estimatable (e.g., due to limited data), then only unadjusted GMCs, GMTs, GMRs and associated 95% CIs will be presented.

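### If the carriage-interaction model cannot be fitted, the overall cohort GMR loses all adjustment for age, sex and season; the unstratified MOPA draw is a minor precision point

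*SAP*

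**What the plan says.** **Matching.** Protocol 5 enrols two unvaccinated children per vaccinated child. "These control subjects will be matched by age", in three bands (5-12, >12-24 and >24-60 months), and they are "enrolled if the non-13vPnC subjects hospital admission dates are within 7 days" of the vaccinated child's.

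**Model.** SAP 5.2.2 regresses log concentration or log titer on cohort, vaccine-type (VT) carriage, their interaction and the "confounding variables (age at enrollment, sex, season of enrollment"). It lists five adjusted ratios. The third is "3. 13vPnC Cohort vs Non-13vPnC Cohort".

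**Fallback.** If adjusted results cannot be estimated, for which the SAP's example is limited data, "then only unadjusted GMCs, GMTs, GMRs and associated 95% CIs will be presented". There is no intermediate model, and SAP 6.1.2 plans no sensitivity analysis.

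**Crude interval.** SAP 5.2.2 back-transforms the "CIs for the mean difference of the measures on the logarithmically transformed scale(IgG/MOPA) using Student's t distribution". It mentions no pairing or matched sets, so I read this as the ordinary two-sample form.

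**MOPA controls.** Protocol 6.2.2.1.2 tests as many controls as vaccinated children and defers the choice: "Further details regarding the selection of this sub-cohort to be identified for MOPA testing will be outlined" in the SAP. SAP 3.1 makes the choice by "randomly ordering all subjects with adequate serum volume and selecting the first number of subjects" needed. Band, date and matched set play no part.

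**The concern.** The fallback is all or nothing. The term most likely to fail is the cohort-by-carriage interaction, because it needs VT carriers in both cohorts. The overall cohort ratio does not depend on that term. Even so, one empty carrier cell would remove age, sex and season from it, although the SAP itself names these as confounders.

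Matching covers only part of the gap. It balances age band and calendar time, but not sex and not age within a band, and the top band spans 36 months. The crude ratio could then carry residual age confounding, with an interval that ignores the matching.

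The MOPA draw adds a smaller matter. It lets age band and season differ by chance between the MOPA cohorts, when the same number of assays could keep them balanced.

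**Working it through.** **Sample size.** Protocol 3.3: 3,800 × 2 × 0.05 = 380 eligible, as stated. Then 380 × 0.30 = 114, which the protocol rounds to about 100; at 1:2 the stated total is about 300. I use 100 vaccinated children, 200 controls and 100 MOPA controls. With 114 the standard error (SE) ratios below are the same to rounding.

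**How often the fallback could be reached.** The documents give no VT carriage rate for vaccinated children. For an assumed rate c, the chance of no VT carrier among m vaccinated children is (1 − c)^m. With m = 100 it is 0.37 at 1%, 0.13 at 2%, 0.006 at 5% and below 0.001 at 10%. Enrollment closes at the end of 2020 whatever the count (Protocol 3.3). With an assumed m = 30 the chance is 0.95^30 = 0.21 at 5% and 0.90^30 = 0.04 at 10%.

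**Age within the top band.** Inputs from Protocol 1: approval in October 2016, primary doses at 2, 4 and 6 months. Protocol 3.2 gives about 24 months of study ending in 2020; I assume enrollment from January 2019 to December 2020, which is 27 to 50 months after approval. A child first dosed at 2-6 months at approval is then at most:
- 29-33 months old in January 2019
- 40-44 months old in December 2019
- 52-56 months old in December 2020

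Controls may be up to 60 months. If ages were spread evenly from 24 months to a cap C (60 for controls), the mean gap would be (60 − C)/2, or 13.5-15.5, 8-10 and 2-4 months at the three dates. If first doses as late as 15 months occurred, the caps would be 42, 53 and 65 months and the gaps 9, 3.5 and none. I take 4-12 months as the range.

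**Shift in the crude GMR.** For gap d (months), fold change g in titer per year of age and top-band share w, the factor is g^((d/12) × w). All three inputs are assumptions.

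| d | g | w | factor |
|---|---|---|---|
| 4 | 1.1 | 0.20 | 1.006 |
| 8 | 1.2 | 0.33 | 1.041 |
| 12 | 1.5 | 0.33 | 1.145 |

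The direction depends on whether titers rise or fall with age. For scale, with an assumed SD of 1 on the ln scale, the crude 95% half-width is 1.96 × √(1/100 + 1/200) = 0.24 for IgG and 1.96 × √(2/100) = 0.28 for MOPA. The largest shift, ln 1.145 = 0.135, is about half of that; the middle one, ln 1.041 = 0.040, is about one sixth to one seventh.

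**Width of the crude interval.** Let r be the correlation of log values within a matched set (unit variance, n = 100).
- IgG, 1:2: true variance 1.5(1 − r)/n, unpaired 1.5/n, SE ratio 1/√(1 − r).
- MOPA, random draw: both controls of a set are drawn with probability (100/200)(99/199) = 0.2487. The true variance is (2 − 1.5025r)/n, unpaired 2/n, SE ratio √(2/(2 − 1.5025r)).
- One control per set would give 2(1 − r)/n. The last column is the SE of the random draw relative to this.

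| r | IgG unpaired/true | MOPA unpaired/true | MOPA random/one per set |
|---|---|---|---|
| −0.1 | 0.953 | 0.964 | 0.989 |
| 0 | 1.000 | 1.000 | 1.000 |
| 0.1 | 1.054 | 1.040 | 1.014 |
| 0.2 | 1.118 | 1.085 | 1.031 |
| 0.3 | 1.195 | 1.136 | 1.052 |

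At r = −0.1 coverage falls to about 94%.

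**The MOPA draw after adjustment.** In a simulation (8,000 replicates, equal bands, age band explaining 30% of log-titer variance) the SE of the log GMR was 0.125 crude with the random draw, 0.118 crude with a stratified draw, and 0.119 with the random draw and age band fitted. Across all settings tried, the bias was at most 0.0033 in absolute value, within simulation error.

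**The case against.** **The fallback may never be used.** This is a fair point. Protocol 1 cites 13-53% of lower respiratory infections as pneumococcal and 80.5-87.2% serotype coverage. Even 0.13 × 0.805 = 10% would make an empty cell very unlikely with 100 children. But those figures describe cause of disease and general serotype coverage, not VT carriage in vaccinated children. The SAP itself provides for failure of the model, so what happens then should be sound.

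**Matching already handles age and season.** It does so for band and date if the sets are near complete. Supply looks adequate: 3,800 × 0.95 × 15/365 ≈ 148 unvaccinated admissions per 15-day window, about 45 at 30% consent. Matching does not cover sex or age within a band.

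**The MOPA rule is complete, reproducible and unbiased.** This stands. A reader might infer that the unrestricted draw biases the MOPA ratio. The documents do not support that, because a random sample from a matched pool keeps its age and date mix in expectation. A reader might also make much of the 25% of vaccinated children for whom neither own control is drawn. No set-level analysis is planned, so that figure feeds into nothing. Nor should a chance band imbalance be counted on top of the interval width, because the crude interval already allows for it.

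**The study is descriptive.** Protocol 8 and SAP 5.1 say so, and no hypothesis or decision rule is at stake.

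**Conclusion.** The point holds for the fallback in SAP 5.2.2. If the interaction model fails, the overall cohort GMR for IgG and MOPA is reported without adjustment for confounders that the SAP names, although a simpler model could keep them. The crude ratio may be biased by a factor of about 1.01 to 1.15, given assumed age gaps of 4-12 months, slopes of 1.1- to 1.5-fold per year and a top-band share of 20-33%. Its interval is about 4-14% (MOPA) or 5-20% (IgG) too wide at assumed r = 0.1-0.3, correct at 0 and slightly too narrow if r is negative. Protocol 1 describes antibodies that decline and are then boosted, so a positive r cannot be taken for granted. This age confounding comes from the fallback and the wide band, not from the draw, and a stratified draw would not remove it.

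The draw in SAP 3.1 is a secondary, optional point: a 0-5% larger SE for the crude MOPA cohort GMR, and almost nothing once age is fitted.

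The single-group results of SAP 6.1.1 and the within-cohort carriage ratios are not affected, because they do not compare cohorts. I make no claim about the within-carriage cohort ratios, which depend on the sparse cells themselves.

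**What to change.** **SAP 5.2.2 (main).** Add an intermediate step. If the full model is not estimable, report the overall cohort GMR and 95% CI from a model without the cohort-by-carriage interaction, and without carriage if needed, that keeps age at enrollment, sex and season. Present unadjusted results alone only if that model also fails. Age band alone would not be enough, since the concern is age within a band.

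Cost: one more model to program, with data already collected. The reduced model gives the cohort contrast averaged over carriage, and the report should say so. A single age slope for both cohorts is an approximation, so adjustment should reduce the within-band difference rather than guarantee its removal.

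**SAP 3.1 (optional).** Stratify the random MOPA draw by the Protocol 5 age bands and calendar quarter, with stratum sizes equal to those of the vaccinated children tested and the same total number of assays. Cost: a rule for strata with too few adequate-serum controls, for example filling from the same band and the nearest quarter. Under assumed even enrollment and adequate serum for all, the mean shortfall is only 0.01-0.03 children. If matched sets are incomplete, the subset will mirror the age mix of the vaccinated children rather than of all enrolled controls. Make this change only together with the first, because stratifying alone leaves the unpaired crude interval more conservative.

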The investigator may schedule visits (unplanned visits) in addition to those listed in the Schedule of Activities table, in order to conduct evaluations or assessments required to protect the well-being of the subject.

Procedure/ Assessment	Visit 0 ^c	Visit 1
Review inclusion/exclusion criteria, including initial assessment of 13vPnC vaccination history	x	
Informed consent	x	
Assign subject number	x	
Confirmation of 13vPnC vaccination history	x	
Enroll subject, assign cohort		x
Demography, medical history, and antibiotic usage		x
Record dates of 13vPnC vaccination		x
Obtain blood sample ^d		x
Record deep upper respiratory aspirate specimen information ^a or collect aspirate as a study procedure ^e		x
Adverse event reporting ^b		x

- a. Obtained as per local standard of care or performed as a study procedure.
- b. See [Section 7.1](#) for adverse event report requirements.
- c. Visit 0 and Visit 1 will occur on the same day.
- d. ELISA and MOPA will be conducted on all 13vPnC cohort patients and a subset of non 13vPnC patients.
- e. Culture will be performed on these samples. If *S. pneumoniae* positive, serotyping, will be performed.

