3. STUDY DESIGN

This is a cohort study designed to describe serotype-specific antibody levels by 13vPnC vaccination status (in children who completed at least 2 doses of 13vPnC, versus children that did not receive any 13vPnC) and vaccine type (VT) carriage status, among children 5 months to \leq 60 months of age with clinical pneumonia. Thus, there will be four subgroups in this study: the 13vPnC cohort with VT carrier; the 13vPnC cohort without VT carrier; the unvaccinated cohort with VT carrier; and the unvaccinated cohort without VT carrier.

Children hospitalized with a diagnosis of clinical pneumonia will be considered for the study. Upon identification of a potential subject, all Inclusion and Exclusion criteria will be reviewed. The vaccination history of 13vPnC will initially be obtained either from the patient's parent/caregiver; confirmation of 13vPnC receipt from vaccine book or image of vaccine book is required. If 13vPnC vaccination is confirmed as received, and all other inclusion/exclusion criteria are met, this child will be enrolled and assigned to the vaccinated group. If 13vPnC vaccination is confirmed as not received, and all other inclusion / exclusion criteria are met, this child may be enrolled and assigned to the unvaccinated group. After the subject is enrolled, the 13vPnC receipt date and history of other vaccination status will be recorded, as well as other medical and demographic information. The blood draw of approximately 5 mL will be performed at this time.

Based on SCH local standard practice, deep upper respiratory aspirates are obtained and cultured for children hospitalized with clinical pneumonia. This may occur before the consent or enrollment. If the aspirate was not obtained as part of standard practice, the aspirate will be collected as a study procedure. Once the subject is enrolled, the sample identification (ID) and culture results for this procedure will be recorded into the case report form (CRF). In SCH all *S. pneumoniae* isolates recovered from hospitalized children regardless of patient age will be serotyped by FuDan University as part of study WI232403. Therefore, any additional ID used to label those *S. pneumoniae* isolates will be entered into the CRF so that the serotype information can be imported into this study database.

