6.2.2. Deep Respiratory Aspirate

Based on SCH local standard practice, deep upper respiratory aspirates are obtained and cultured for children hospitalized with clinical pneumonia. This may occur before enrollment. If a deep respiratory aspirate was not collected as a standard practice, an aspirate sample will be collected as a study procedure.

The aspirates will first be cultured at SCH laboratory, in appropriate culture medium that supports the growth of *S. pneumoniae*. If *S. pneumoniae* is isolated, serotyping will be performed at Fudan University as part of study WI232403.

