6.2.2.1.1. ELISA Assessments

Serum concentrations of anticapsular IgG will be determined by ELISA for each of the 13 pneumococcal serotypes (1, 3, 4, 5, 6A, 6B, 7F, 9V, 14, 18C, 19A, 19F, and 23F) in all subjects with a collected blood sample.

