2.1.1. Primary Estimand

The serotype-specific IgG geometric mean concentration (GMC) and MOPA geometric mean titers (GMT) for each of the pneumococcal serotypes measured at the time of diagnosis of clinical pneumonia

The primary estimand of this study will be the GMC and GMT for each cohort (refer to section 2.2 for each cohort). The estimand is defined according to the primary objective and is in alignment with the primary endpoint. It includes the following 2 attributes:

- Population: Patients who meet all study inclusion/exclusion criteria;
- Variable: IgG /MOPA;

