6.1. Primary Endpoint(s)

6.1.1. Primary Analysis

For each cohort, children will be assigned to 2 groups: Participant in whom a 13vPnC vaccine type (VT) strain has been isolated from the respiratory tract, and participant from whom a 13vPnC VT strain has not been isolated from the respiratory tract (VT carrier versus without VT carrier). Therefore, a total of 4 subgroups are available: 13vPnC cohort with VT carrier; 13vPnC cohort without VT carrier; unvaccinated cohort with VT carrier; unvaccinated cohort without VT carrier.

For each of the 13 serotypes contained in 13vPnC, the IgG concentration and MOPA titers will be transformed in logarithm scale. Crude (unadjusted) geometric mean concentrations (GMCs) and geometric mean titers (GMTs) and 95% confidence interval (CI) will be calculated for the 4 cohort/carriage subgroups.

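### Does a MOPA draw that ignores VT carriage wrongly leave half of the unvaccinated carriers untested?

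*SAP*

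**What the plan says.** Protocol Section 6.2.2.1.2 has MOPA done in every vaccinated child with enough blood and in an equal number of unvaccinated children. It leaves the method of selecting the latter to the SAP. SAP Section 3.1 supplies it: "randomly ordering all subjects with adequate serum volume and selecting the first number of subjects", until the vaccinated number is matched.

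SAP Section 2.1.1 states the target: "The primary estimand of this study will be the GMC and GMT for each cohort". SAP Section 6.1.1 adds that crude means with confidence intervals "will be calculated for the 4 cohort/carriage subgroups". SAP Section 5.2.2 lists five adjusted ratios. Three matter most here:

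- comparison 2: carriers versus non-carriers among the unvaccinated;
- comparison 4: "Within VT-carrier +: 13vPnC Cohort vs Non-13vPnC Cohort";
- comparison 5: the same contrast among non-carriers.

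For IgG, Protocol Section 6.2.2.1.1 provides ELISA "in all subjects with a collected blood sample". Protocol Section 3.3 sets the sample size by feasibility, and SAP Section 5.1 has no hypotheses.

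**The concern.** Carriage is one of the two factors in the study objective, and VT carriers may be the smaller group. A draw that ignores carriage can leave few unvaccinated carriers with a MOPA titer, while serum from other carriers is already in store. Comparison 2 depends mainly on that number, and comparison 4 partly. If the half left untested were an avoidable result of the random ordering, the plan would be giving away precision in subgroups that its own primary analysis reports, and carriers-first selection would recover it with no extra child, blood or assay.

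**Working it through.** **Enrolment (Protocol Section 3.3).** 3,800 × 2 years × 5% = 380 eligible vaccinated children, as stated. 380 × 30% = 114, which the protocol gives as about 100. At 1:2, 100 × 3 = 300 in total, so 200 unvaccinated.

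**Where the half comes from.** Untested share = 1 − 100/200 = 50%. With 114 and 228 it is again 50%. The carriage rate does not enter, and the expected share is the same for non-carriers. A draw stratified in proportion to carriage would also leave half of the carriers untested; compared with the mean standard error (SE) of the planned draw, it improves comparison 2 by only about 1 to 2%. The quota therefore causes the loss. If fewer controls are enrolled, the share falls: 1 − 100/150 = 33%, 1 − 100/120 = 17%.

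**Validity.** A simple random sample of the unvaccinated children is, within each carriage group, a simple random sample of that group. The subgroup and cohort means are therefore all unbiased for the children with adequate serum, without weights.

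**What carriers-first would change.** Assume 100 vaccinated, 200 unvaccinated, 100 unvaccinated assays, equal standard deviations (SDs), and the same carriage rate p in both cohorts. The SE of a log ratio is proportional to √(1/n₁ + 1/n₂). The planned draw tests 100p carriers and 100(1 − p) non-carriers; carriers-first tests 200p and 100 − 200p. The weighted unvaccinated cohort mean changes by √(100 × [p²/k₁ + (1 − p)²/k₀]), where k₁ and k₀ are the carriers and non-carriers tested. The last four rows are SE ratios, carriers-first over planned draw.

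| | p = 10% | p = 15% | p = 20% |
|---|---|---|---|
| Carriers tested, planned draw (95% range) | 10 (6–14) | 15 (10–20) | 20 (14–26) |
| Carriers tested, carriers-first | 20 | 30 | 40 |
| Comparison 2 | 0.750 | 0.779 | 0.816 |
| Comparison 4 | 0.866 | 0.866 | 0.866 |
| Comparison 5 | 1.031 | 1.052 | 1.080 |
| Unvaccinated cohort mean | 1.031 | 1.052 | 1.080 |

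Worked at 20%:

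- Comparison 2: √[(1/40 + 1/60)/(1/20 + 1/80)] = √(0.0417/0.0625) = 0.816.
- Comparison 5: √[(1/60 + 1/80)/(1/80 + 1/80)] = √(0.0292/0.0250) = 1.080.
- Cohort mean: √(100 × [0.04/40 + 0.64/60]) = √1.167 = 1.080.

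**How firm the gain is.**

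- *Carriage rate.* The documents give none. Their nearest figures are the *S. pneumoniae* share of lower respiratory infections (13 to 53%, Protocol Section 1) and serotype coverage (80.5 to 87.2%, same section). Multiplied, they span 0.13 × 0.805 = 10% to 0.53 × 0.872 = 46%, a very indirect guide. Without a cap, comparison 2 is worse from a carriage of about one third upward. At 40% its ratio is √[(1/80 + 1/20)/(1/40 + 1/60)] = 1.22, and that of comparison 5 is 1.41.
- *Equal SDs.* At 20% carriage, if the carriers' SD is half that of non-carriers, the comparison 2 ratio is √[(0.25/40 + 1/60)/(0.25/20 + 1/80)] = 0.957. The gain is then 4% instead of 18%. With double the SD it is 26%.
- *Carriage among the vaccinated.* If it is half the unvaccinated rate, the comparison 4 gain falls from 13% to 9%.
- *Weights.* Without weights, oversampling carriers would bias the unvaccinated cohort mean. If carriers' titers are twice as high, it shifts by a factor of 2^(0.20 − 0.10) = 1.07 at 10% carriage and 2^(0.40 − 0.20) = 1.15 at 20%.

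**The case for a change.** The strongest case for a change is that carriage stands in the objective, in the primary analysis and in four of the five listed ratios, and that SAP Section 5.2.2 itself foresees adjusted estimates failing for lack of data. Capping carriers at half of the assays and applying the rule only when carriage is at most 20% would remove the harm at high carriage. At 15% carriage and an assumed log10 SD of 0.5 to 0.8, the 95% confidence factor for comparison 2 would go from 1.9–2.8 to 1.6–2.2. That arithmetic stands, and a sponsor could reasonably choose such a rule.

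It does not make the planned draw wrong. The gain goes to two subgroup contrasts, and the named primary estimand and comparison 5 pay for it. The cohort-level MOPA summaries would need weights and a stratified variance in place of the planned Student's t intervals. Comparison 3 would turn on an averaging rule that the SAP does not state. Averaged equally over carriage groups, its SE falls by 12% at 10% carriage and 9% at 20%; averaged at observed carriage, it rises by 2% and 4%. Selection by VT status would also have to wait for serotypes, since "serotyping will be performed at Fudan University as part of study WI232403". Selection on the culture result in the CRF avoids the wait, but then the unvaccinated non-carrier group needs weights as well.

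A second argument is that IgG may be affected too, because footnote d of the Protocol's Schedule of Activities reads "ELISA and MOPA will be conducted on all 13vPnC cohort patients and a subset of non 13vPnC patients". Taken alone, it could restrict ELISA as well. It can also be read as saying that the two assays together are done in all vaccinated children and some unvaccinated ones. The dedicated ELISA section covers every child with a blood sample, and SAP Section 3.1 restricts only MOPA. The footnote could be worded more clearly, but the plan gives IgG for unvaccinated carriers.

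**Conclusion.** The concern does not hold. An expected 50% of unvaccinated VT carriers go without a MOPA result if 1:2 enrolment is reached and adequate serum is equally common in both cohorts; with adequacy between 80 and 100% and differing by cohort, the share among carriers with adequate serum is 37.5 to 60%. That follows from testing equal numbers, and it affects non-carriers equally. The draw introduces no bias, needs no weights, and suits the cohort-level estimand of a descriptive study with no precision target.

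Carriers-first selection is a different trade-off. With equal SDs, equal carriage in both cohorts and 10 to 20% carriage, it gains 25 to 18% on comparison 2 and 13% on comparison 4, and loses 3 to 8% on comparison 5 and on the unvaccinated cohort mean. The balance depends on a carriage rate and on SDs that the documents do not supply. Statisticians may reasonably differ on it, and the plan's choice is sound as written.
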